1.5 Exclusion Criteria

- (1) Clinical signs, symptoms, or personal history of CVD
- (2) Diabetes mellitus or fasting serum glucose >140 mg/dL
- (3) Plasma triglyceride levels ≥ 500 mg/dL
- (4) Uncontrolled hypertension (systolic blood pressure >160 mmHg or diastolic blood pressure >110 mmHg)*
- (5) Uncontrolled tachycardia or irregular heart rates (i.e., atrial fibrillation)
- (6) Thyroid disease (untreated)
- (7) Renal insufficiency (defined as serum creatinine >2.0 mg/dL)
- (8) Life threatening illness with prognosis <5 years
- (9) Current use of lipid-lowering medication
- (10) Current use of food supplements containing soy, soy protein, isoflavones or other phytoestrogens
- (11) Known sensitivity or allergy to soy or nuts
- (12) Regular aspirin or other antiplatelet medication use
- (13) Use of anticoagulants
- (14) Bleeding diatheses or tendencies

*Participants who enter screening with a systolic blood pressure >160 mmHg or diastolic blood pressure >110 mmHg will be immediately referred to their physician or to an emergency room. Once the blood pressure is controlled, the participant will become eligible for the trial. Participants who enter screening with mild to moderate hypertension (systolic blood pressure ≤ 160 mmHg or diastolic blood pressure ≤ 110 mmHg) will be notified immediately and a letter issued to the participant and to the participant's physician. Control of hypertension is a requisite to continue into the trial.

1.6

Trial Clinic Flow

- Fasting blood samples drawn for:
 - Chemistry (FSG \leq 140 mg/dL; serum creatinine \leq 2.0 mg/dL)
 - CBC
 - Platelet count
 - Prothrombin time (PT)
 - activated partial thromboplastin time (aPTT)
 - Lipids (triglycerides $<$ 500 mg/dL)
 - C-reactive protein (CRP)
 - Hemoglobin A1c

Draw and store at -80°C (analyze only when eligible):

- Insulin
- Inflammatory markers
 - MCP-1
 - IL-8
 - TNF α
 - IL-1 β
 - IL-10
 - E-Selectin
 - P-Selectin

↓

↓

Schedule randomization visit appointment

8 hour fast

↓

[figure not shown]
↓

Final Eligibility

- Final Eligibility Check List **[Form 17]**
 - ↓
 - ↓

Randomization Visit (v00)

- Nonstudy Medications Record **[Forms 13,14]**
- History of Vitamin and Nutritional Supplement Use Questionnaire **[Form 15]**
- Dietary Food Frequency **[Form 18]**
- Soy Food Questionnaire **[Form 19]**
- 7-Day Physical Activity Questionnaire **[Form 20]**
- Center for Epidemiologic Studies Depression (CES-D) Scale **[Form 21]**
- Cognitive assessment **[Form 22]**

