9.6.3 Comparison of On-trial Changes in Laboratory and Lifestyle Variables

Treatment groups will be compared with respect to on-trial levels and on-trial changes in plasma insulin, lipids/CRP, hemoglobin A1c, coagulation factors, rheology parameters and inflammatory variables. Study groups will also be compared for on-trial levels and on-trial changes of other factors that might confound the analysis of primary end point differences. These will include analysis of dietary factors (e.g., total calories, and total calorie-adjusted calories from total, saturated, polyunsaturated, and monounsaturated fats, calories from protein, calories from carbohydrates, and dietary genistein, daidzein, and glycitein), physical activity, cardiovascular risk factors (including blood pressure, smoking status), and use of relevant nonstudy medications (including antihypertensive and lipid-lowering medications). For descriptive purposes, on-trial laboratory, dietary, clinical, and physical activity variables will be computed as the average of all on-trial determinations, weighted by the length of time between determinations. On-trial smoking will be compared as percentage of smokers versus percentage abstainers; average on-trial smoking levels (cigarettes per day) will also be computed for smokers as the average of all on-trial determinations as above. For all laboratory and clinical measures, a change variable will be computed at each on-trial measurement time as: on-trial value minus baseline value. Changes in laboratory and clinical variables from baseline will be compared within each treatment arm using generalized estimating equations to account for the repeated measurements over the study period; the model-specified correlation structure of the repeated measures will be determined by examination of the observed correlation structure. The test that the model intercept differs from 0 will comprise the overall test for significant change from baseline; incorporation of covariates for time periods of the study will test for differential change from baseline over the study period. Comparison of on-trial levels and changes in laboratory and clinical variables across treatment groups will also use generalized estimating equations, with an added covariate for randomized treatment group; interaction terms of treatment group-by-study time period will test whether treatment group differences vary over the study period. Compliance with the study product will be compared across treatment groups, also using generalized estimating equations as described. All analyses will be performed for the entire study sample and for the group of participants whose overall study product compliance is $>80\%$. The significance level for all analyses will be set at a two-sided $\alpha=0.05$.

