9.6.5.1 Primary Efficacy Analysis: Carotid Artery IMT Analyses

The primary end point will be the per-subject rate of change in the right distal CCA far wall IMT. The rate of change in the right distal CCA far wall CIMT will be computed for each participant by fitting a regression line of CIMT on years since baseline ultrasound. The estimated slope of the regression line will be used as that subject's CIMT rate of change. Analyses of trial end points will be performed on the intent-to-treat sample, which will be defined as all randomized participants who had a baseline and at least 1 follow-up CIMT measurement taken after randomization.

The statistical approach outlined above will be accomplished using mixed effects models for longitudinal data, with the randomization stratification variable (dichotomized baseline CIMT) used as a covariate. Each CIMT measure will be included as a dependent variable. The regression coefficient associated with the model covariate of time on-study will estimate the average group progression rate of CIMT (in mm/year). Random effects terms for the regression intercept and slope (change over time) will allow for individual participant deviations from their group average in baseline CIMT and CIMT rate of change, respectively. The statistical test for differences in the CIMT rate by treatment group will be accomplished by adding a treatment group by time on-study interaction term. The significance of the regression coefficient associated with this interaction term is the test that the CIMT rates differ by treatment group. We will also evaluate baseline plasma levels of insulin, lipids/CRP, hemoglobin A1c, coagulation factors, rheology parameters and inflammatory variables, dietary nutrients, smoking, blood pressure, physical activity and use of non-study medications as potential confounders. If any of these variables are found to be confounders of treatment-rate of CIMT relationship, they will be included as

covariates in the analysis.

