9.6.5.2 Co-Primary Efficacy Analysis: Carotid Artery Stiffness Analyses

Statistical methods to evaluate the arterial stiffness outcomes will mirror those specified for the CIMT analyses above. A normalizing transformation will be applied to the arterial stiffness measures prior to analysis if required.

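### The primary slope model names covariates without covariate-by-time terms, so on its natural reading the promised adjustment of the CIMT rate does not happen

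*Combined protocol and SAP*

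**What the plan says.** Section 9.6.5.1 defines the primary end point as each participant's CIMT slope and says the analysis is carried out with a mixed model that has random intercepts and slopes, "with the randomization stratification variable (dichotomized baseline CIMT) used as a covariate". On the test it states: "The significance of the regression coefficient associated with this interaction term is the test that the CIMT rates differ by treatment group". The interaction meant is treatment group by time on study, and it is the only interaction named in the section.

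The section then lists baseline plasma and other laboratory measures, dietary nutrients, "smoking, blood pressure, physical activity and use of non-study medications as potential confounders", and continues: "If any of these variables are found to be confounders of treatment-rate of CIMT relationship, they will be included as" covariates. It does not say what counts as being found a confounder, or whether a selected covariate also gets a by-time term.

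Section 9.6.5.2 extends this to the co-primary: "Statistical methods to evaluate the arterial stiffness outcomes will mirror those specified for the CIMT analyses above".

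Section 9.6.7.4, an ancillary analysis, does write out time-by-covariate interactions where an association with the CIMT rate is wanted.

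**The concern.** The quantity tested is a difference in slopes. In a random intercept and slope model, a baseline covariate entered as a main effect explains differences in CIMT level. To explain differences in rate, it must be multiplied by time. The plan says it will adjust for confounders of the relation between treatment and rate, but the only form of entry it names is a covariate. Because section 9.6.7.4 spells out by-time terms and section 9.6.5.1 does not, a programmer would most naturally code main effects. That is an inference, since the text does not say so outright.

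If it is coded that way, both co-primary analyses would be reported as adjusted while the tested coefficient is not. Precision available from baseline predictors of progression would be lost, and chance imbalance in those predictors would remain in the estimate.

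**Working it through.** **Plan's own figure.** The sections reviewed give no slope SD, effect size or dropout rate for the primary end point, so there is no figure to reproduce. The structural result below does not depend on the assumed variances; the sizes do.

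**Inputs from the documents.** 240 participants (1.3). Eight scans: the screening visit about two weeks before v00 (3.3), v00, and months 6, 12, 18, 24, 30 and 36 (9.3.3). Visit window ±14 days (9.5.2.2). Scan CV below 3% (8.3.2); at the 0.75 mm stratum cut-point (4.2) that is an error SD of at most 0.03 × 0.75 = 0.0225 mm.

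**Assumptions.** Equal arms, error SD 0.022 mm, slope SD 0.012 mm/yr, between-person SD 0.10 mm, and one baseline factor with correlation ρ of 0.2 to 0.4 with the slope.

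**1. Structure.** With complete data at common times and a treatment main effect (not named in 9.6.5.1, but standard), the model is a pair of regressions, one for participants' intercepts and one for their slopes. Adding a covariate to the intercept equation alone leaves the slope-equation estimate unchanged.

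*One simulated trial fitted by REML* (slope SD 0.010 mm/yr, error SD 0.0225 mm, factor explaining 20% of slope variance, imbalance 0.25 SD):

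| Model | Treatment × time, µm/yr (SE) |
|---|---|
| No covariate | 1.873 (1.710) |
| Covariate main effect | 1.873 (1.710) |
| Covariate main effect and × time | 0.437 (1.554) |
| Per-subject slopes on treatment and covariate | 0.437 (1.554) |

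*Repeated trials* (150 per setting, slope SD 0.012, ρ = 0.3, variance components known):

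- Complete data: the main effect moves the contrast only by rounding error (below 10⁻¹² SE). The by-time term moves it by 0.21 to 0.22 SE on average and by up to 0.98 SE.
- 15% loss with ±14-day jitter: the main effect moves it by 0.03 to 1.4% of an SE on average, at most 4.5%. The range covers a factor unrelated to the intercept and one correlated 0.3 with it (intercept-slope correlation 0.2).
- 30% loss with jitter: mean at most 1.9%, largest 6.9%.
- A harsher setting with 40% loss gave single shifts of up to 0.23 µm/yr against an SE of 1.83 (13%), but on average captured only about 1 to 2% of the adjustment made by the by-time term.
- With the treatment main effect left out: mean shift 0.1 to 3% of an SE, at most 16%.

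**2. Precision forgone.** Sxx for the eight times is 9.07 yr². Error variance of a fitted slope = 0.022² / 9.07 = 0.0000534. Reliability = 0.012² / (0.012² + 0.0000534) = 0.000144 / 0.0001974 = 0.73. SE of the contrast = √(0.0001974 × 4/240) = 0.00181 mm/yr = 1.81 µm/yr.

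SE cut from a by-time term = 1 − √(1 − 0.73ρ²): 1.5% at ρ = 0.2, 3.3% at 0.3 and 6.0% at 0.4. Over slope SDs of 0.006 to 0.015 the ranges are 0.8 to 1.6%, 1.8 to 3.7% and 3.3 to 6.7%.

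**3. Chance imbalance.** The SD of the arm difference in a standardized factor is √(4/240) = 0.129 without adaptation. If the corrections in 4.2 balanced the first 200 perfectly and the last 40 were left to chance, it is √40/120 = 0.053. An imbalance above 0.20 SD then occurs in 12% or 0.01% of trials, and above 0.10 SD in 44% or 6%.

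An imbalance of 0.20 SD shifts the contrast by ρ × 0.012 × 0.20, that is 0.48 to 0.96 µm/yr (0.26 to 0.53 SE). Given that imbalance, the unadjusted test's two-sided error is 5.5 to 6.8%. At 0.10 SD it is 4.5 to 4.9%, no higher than nominal.

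**4. Related wording.** Section 9.6.7.2 gives the modifier term as treatment by subgroup, without time. In 9.6.3 the between-arm GEEs for change name no baseline value, whereas 9.6.5.3 includes one for cognition. For one follow-up at unit variance and baseline correlation r, the change score has variance 2 − 2r and the baseline-adjusted analysis 1 − r²: 1.00 against 0.75 at r = 0.5, and 0.60 against 0.51 at r = 0.7, so 25% and 15% lower.

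**The case against.** **The intent is plain.** The end point is the per-subject slope, the mixed model is said to carry out that approach, and confounders are sought for the relation with the rate. If covariates entered a regression of the slopes, the adjustment would work. This stands as far as it goes. On that reading the stratum is a named, unconditional covariate, so one cannot say that no reading gives a prespecified adjusted rate. The remaining covariates would still be selected by an unstated rule after seeing the data, and the mixed model still needs explicit by-time terms to do the same job.

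**The effect is small.** Also true. Randomization protects the unadjusted test, and the adaptive corrections in 4.2 may remove most imbalance.

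Some stronger readings are tempting but not supported:

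- *The primary test is invalid or its error is inflated.* It is not. The conditional errors above average out over trials to 5%.
- *On-trial values will enter the primary model.* The word baseline sits next to plasma levels, the lifestyle items follow it unqualified, and 9.6.3 compares "on-trial levels and on-trial changes of other factors that might confound the analysis of primary end point differences", including "use of relevant nonstudy medications (including antihypertensive and lipid-lowering medications"), although 1.5 excludes "Current use of lipid-lowering medication". But baseline most naturally governs the whole list, 9.6.3 only compares these factors between arms, and 9.6.7.1 and 9.6.7.3 place on-trial values in ancillary and mediation analyses. One clarifying sentence is enough.
- *A search over dozens of named candidates seriously inflates error.* Section 9.6.5.1 names categories, and a detailed count has to borrow illustrative items from 9.6.3. Under ordinary selection rules, simulated null error with 43 candidates was 4.3 to 7.3%. The problem is the unstated rule.
- *The modifier tests have almost no power.* That follows only if the phrase in 9.6.7.2 is taken literally. It refers to differences in treatment effect within the efficacy models, where the effect on a rate is already treatment by time, so it is probably shorthand.
- *Age is overlooked.* It is compared at baseline (9.6.2) and tested as a modifier (9.6.7.2). It is only missing from the confounder list in 9.6.5.1.

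**Conclusion.** The point holds at minor to moderate severity. Taken as written and on its natural reading, the plan promises an adjusted rate comparison and delivers an unadjusted one for both co-primary end points. That structural result is exact with complete data, common visit times and a treatment main effect, and close to exact otherwise.

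The consequence is modest. The test keeps its 5% level. The SE is about 1.5 to 6% larger than it need be for a factor correlated 0.2 to 0.4 with the slope, and a chance imbalance of 0.20 SD would leave a shift of about a quarter to a half of an SE. The correlations, slope SD and loss rates are assumptions. No size is given for arterial stiffness, because the sections reviewed provide no slope variance for it.

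**What to change.** 1. In 9.6.5.1, and by reference in 9.6.5.2, specify the model: time, treatment, treatment × time, stratum, stratum × time, and a short fixed list of pre-randomization covariates, each as a main effect and × time. The balance factors of 4.2 (age, LDL-C, smoking, blood pressure) are an obvious list, though the documents do not show that they predict the slope. ANCOVA of per-subject slopes on the same terms is an acceptable alternative. Centre the covariates, or report marginal slopes, so that the time coefficient keeps its stated meaning as an average progression rate. Confirm that the blood pressure term suits the stiffness measures, which are divided by pulse pressure (9.3).
2. State that only pre-randomization values enter the primary model. Make the confounder-selection step a sensitivity analysis, also with × time terms, with its candidates and criterion fixed before unblinding.
3. Minor: in 9.6.7.2 write the modifier test for rate end points as treatment × subgroup × time with all lower-order terms. In 9.6.3 add each variable's baseline value to the between-arm GEEs, as 9.6.5.3 does for cognition.

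Cost: SAP wording only, since the variables are already collected at SV or v00. With smoking as yes/no and one blood pressure measure, the primary model gains 1 (stratum × time) + 4 × 2 = 9 fixed-effect parameters, affordable with 240 participants.

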9.6.5.2 Co-Primary Efficacy Analysis: Carotid Artery Stiffness Analyses

Statistical methods to evaluate the arterial stiffness outcomes will mirror those specified for the CIMT analyses above. A normalizing transformation will be applied to the arterial stiffness measures prior to analysis if required.

9.6.5.3 Secondary Efficacy Analysis: Cognition Analyses

Three composite cognitive measures will be used to test for randomized treatment group differences in cognition; each composite will be considered as co-secondary endpoints. (1) The global composite will use scores from all neuropsychological tests. (2) The verbal memory composite will use the California Verbal Learning Test and East Boston Memory Test immediate and delayed recall scores. (3) The executive function composite (determined from principal components of prior trial data) will use scores from the Symbol Digit Modalities Test, the Trail Making Test, the Shipley Abstraction scale, Letter-Number Sequencing, and category fluency. The composites will be calculated as the average of component standardized scores weighted by the inverse interest correlation matrix. Absolute values of change from baseline on each cognitive endpoint will be calculated at both post-randomization cognitive follow-ups (18 and 36 months). General estimating equation models will be used to analyze the repeated measures of change in the cognitive endpoints. The primary independent variables will be randomized treatment group; covariates will include the CIMT randomization stratification variable as well as the baseline value of the cognitive endpoint. Differences in cognitive change will be tested by treatment group. Further analyses will test for interactions with test time (18 versus 36 months) to evaluate whether treatment effects (treatment by time interaction) vary by follow-up time.

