1.1 Executive Summary

The potential for nattokinase to “thin” blood and to reduce blood clotting by positive antithrombotic and fibrinolytic effects presents a unique opportunity to safely study such effects on cardiovascular disease (CVD) and cognition. Unfortunately, such studies of antithrombotic and fibrinolytic pathways of prevention have been limited due to lack of safe compounds and the adverse reactions associated with current agents such as Coumadin. Nattokinase, an over-the-counter supplement used for cardiovascular health, is the most active functional constituent of natto, a fermented soy product. Natto has been consumed primarily by the Japanese for over 1000 years, a population with one of the lowest risks for CVD and dementia. CVD and dementia remain the most challenging age-related health risks of the 21st century for Americans necessitating development of further effective preemptive strategies. Whether reducing the propensity for thrombus formation and/or increasing fibrinolytic activity can prevent the progression of atherosclerosis and cognitive decline has not yet been determined.

Using nattokinase under primary prevention conditions, we propose to conduct a randomized, double-blinded, placebo-controlled trial to determine whether decreasing atherothrombotic risk can reduce the progression of atherosclerosis and cognitive decline. We propose to randomize 240 healthy non-demented women and men to nattokinase supplementation or to placebo for three years. The primary trial end points will be measurement of carotid arterial wall thickness and arterial stiffness, early changes of atherosclerosis that can be measured safely by non-invasive imaging techniques. The secondary trial end point will be ascertained through change in cognition measured by a neuropsychological battery. In addition, biochemical blood measurements and in vitro studies will be conducted to compare the effects of nattokinase relative to placebo on blood coagulation and thrombus break-down capabilities, blood flow properties, inflammation and inflammatory activation of endothelial cells that line blood vessels.

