At the conclusion of this trial, we expect to have sufficient evidence as to whether reducing propensity for thrombus formation and/or increasing fibrinolytic activity can prevent atherosclerosis progression and cognitive decline. Results will provide novel and important data that will be informative concerning primary prevention through the atherothrombotic pathway. Providing evidence for a reduction in atherosclerosis progression and cognitive decline with nattokinase is likely to shift the current clinical paradigm for the prevention of these chronic age-related processes. Additionally, such evidence will serve to create a new field of discovery and opportunity for prevention of CVD and dementia.

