1.3 Study Overview

The Nattokinase Atherothrombotic Prevention Study (NAPS) is a randomized, double-blinded, placebo-controlled, non-invasive vascular imaging trial. A total of 240 healthy non-demented women and men without clinical evidence of CVD or diabetes mellitus will be randomized to either placebo or to active oral nattokinase 2,000 fibrinolytic units daily. Recruitment will occur over 2 years and the treatment period will be for 3 years. Candidates will be prescreened, seen for 1 screening visit to determine eligibility and then randomized at a baseline visit. Participants will then return for a follow-up visit 1 week after randomization and then will be followed monthly for the first 6 months and then every 3 months for the remainder of the trial. Rate of change in distal common carotid artery (CCA) far wall intima-media thickness (CIMT) and arterial stiffness in computer image processed B-mode ultrasonograms will be the co-primary trial end points. Cognitive decline determined with a neuropsychological battery designed to evaluate 7 cognitive domains including: attention, concentration, working memory, executive function; visuospatial/visuoconstructive skills; naming/semantic memory; and verbal and nonverbal episodic memory will be the secondary trial endpoint. Other endpoints will include blood pressure, hemostatic, fibrinolytic and hemorheological factors as well as platelet activity and biomarkers for inflammation, monocyte activation, vascular endothelium injury and activation of vascular endothelium by circulating monocytes.

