9.6.7 Ancillary Statistical Analyses

9.6.7.1 Within-Group Analyses

The effects of on-trial end point variables other than treatment modality on the per-subject rate of change in CIMT, arterial stiffness and cognition will be separately assessed. The parameters to be tested will include laboratory data (plasma insulin, lipids/CRP, hemoglobin A1c, coagulation factors, rheology parameters, inflammatory variables and nattokinase levels), clinical variables (blood pressure, body mass, waist:hip ratio, etc.), and lifestyle variables (dietary intake, physical activity, smoking, etc.). Baseline and on-trial values of these data will be collected in order to address questions of clinical significance within each treatment group such as: 1) which baseline characteristics have differential effectiveness on the rate of change in CIMT; and, 2) what is the role of changes in these variables on the rate of change in CIMT. These analyses will utilize mixed effects models and generalizing estimating equations with CIMT (arterial stiffness, cognition) as the dependent variable. Analyses will be conducted in the combined sample with a covariate included to control for treatment group. Interaction terms with treatment group will be introduced to test whether relationships between independent variables and the trial end point are of equal magnitude between the 2 study groups. Experiment-wise error rates in these analyses will be controlled. All participants contributing at least one follow-up ultrasound (or cognitive test) will be included in these analyses.

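### Section 9.6.5.3 tests three co-secondary cognitive composites with no stated order, success rule or error control, though cognition carries half of the main hypothesis

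*Combined protocol and SAP*

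**What the plan says.** The summary sections speak of cognition in the singular. Section 1.1 states: "The secondary trial end point will be ascertained through change in cognition measured by a neuropsychological battery". Section 1.3 lists the domains of the battery, ending with the words "verbal and nonverbal episodic memory will be the secondary trial endpoint".

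Section 9.6.5.3 gives the working definition: "Three composite cognitive measures will be used to test for randomized treatment group differences in cognition", and "each composite will be considered as co-secondary endpoints". Each composite is analysed as repeated change from baseline at 18 and 36 months and tested by treatment group. The composites overlap: "The global composite will use scores from all neuropsychological tests", while verbal memory and executive function each use a subset of those tests.

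Two other sentences touch on error control, and neither reaches these tests:

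- Section 9.6.7.1 says "Experiment-wise error rates in these analyses will be controlled". The analyses meant are ancillary ones, on variables other than treatment.
- The Lan-DeMets rule in 9.6.6 applies to safety data. That section also rules out interim looks at cognition.

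Two-sided 0.05 is stated in 9.6.2 and 9.6.3 for the analyses of those sections. Section 9.6.5 states no level.

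**The concern.** Cognition is not exploratory in this plan. Hypothesis 1 in section 1.2 pairs it with atherosclerosis progression, and section 1.1 expects enough evidence to say whether the mechanism "can prevent atherosclerosis progression and cognitive decline".

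Three tests of equal rank can disagree. If only executive function reaches significance, the plan does not say whether the cognitive hypothesis is supported, unsupported or undecided. That choice would be made after the results are known, and the most favourable reading is that any one composite suffices. On that reading the family-wise error exceeds the level of each test.

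The gap also carries forward: the mediation analysis (9.6.7.3) and the correlation analysis (9.6.7.4) use the cognitive composites without naming a lead one.

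**Working it through.** The available text gives no family-wise error or power figure for cognition, so there is nothing to reproduce.

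**Inputs**

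- Tests: 3 (9.6.5.3). The treatment-by-time tests in the same section are not counted.
- Level: two-sided 0.05 each. Assumed, from 9.6.2 and 9.6.3.
- Decision rule: any one significant composite counts. Assumed; the plan states no rule.
- Interim looks at cognition: none (9.6.6).
- Composition: 14 tests listed in 9.4.2; 2 of them in verbal memory and 5 in executive function, with no test in both; all 14 in the global score.
- Correlations: not given. A common inter-test correlation r of 0.2 to 0.5 in the change scores is assumed.

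**Step 1: independence limit.** 1 - (1 - 0.05)^3 = 1 - 0.857 = 14.3%. The global score contains the other two, so this limit cannot be reached.

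**Step 2: correlations implied by overlap.** For a composite of *a* tests inside one of *n*, the correlation is sqrt[(a/n)(1 + (n-1)r)/(1 + (a-1)r)]. For two composites of *a* and *b* tests with none shared, it is r·sqrt(ab)/sqrt[(1 + (a-1)r)(1 + (b-1)r)].

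At r = 0.3:

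- Global-verbal: sqrt[(2/14)(4.9/1.3)] = 0.73.
- Global-executive: sqrt[(5/14)(4.9/2.2)] = 0.89.
- Verbal-executive: 0.3·sqrt(10)/sqrt(1.3 × 2.2) = 0.56.

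When all inter-test correlations are equal, the inverse-correlation weights of 9.6.5.3 reduce to equal weights, so simple averages are exact here.

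**Step 3: false-positive rates.** Simulation of three correlated normal statistics under no effect (at least 2 million draws), with the critical value 1.96:

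| r | Global-verbal | Global-executive | Verbal-executive | Any false difference | Any false benefit (nominal 2.5%) |
|---|---|---|---|---|---|
| 0 | 0.38 | 0.60 | 0.00 | 13.0% | 6.6% |
| 0.2 | 0.65 | 0.85 | 0.43 | 10.9% | 5.5% |
| 0.3 | 0.73 | 0.89 | 0.56 | 10.2% | 5.1% |
| 0.5 | 0.85 | 0.94 | 0.75 | 8.9% | 4.4% |
| 0.6 | 0.89 | 0.96 | 0.81 | 8.3% | 4.2% |

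**Step 4: sensitivity.**

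- Counting 17 scores, with 4 in verbal memory (immediate and delayed recall on two tests) and 5 in executive function, gives 10.4% at r = 0.2 and 8.3% at r = 0.5. For false benefit the figures are 5.2% and 4.2%.
- With 17 scores correlated 0.4 within the two domains and 0.2 elsewhere, simple averages give 11.0% and inverse-correlation weights 11.6%. The upper edge of the range is therefore soft.
- If all three composites were correlated 0.95 with one another, the rate would be 7.4%.

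**Step 5: after a rule is added.**

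- *Global first.* If the global null is true, any false claim needs a false global rejection, so the error is at most 5%. If it is false, Holm across the other two holds 5%.
- *Holm across three.* The first threshold is 0.05/3 = 0.0167. With no effect on any composite, the error is 4.9% if they are independent, 4.4% at correlation 0.5 and 3.0% at 0.9.

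**The case against.** The strongest reply is that the plan never says one significant composite is enough. If co-secondary meant that all three must succeed, the error would be at most 5%. This stands: the defect in the text is the missing rule, and the inflation is conditional on the any-one reading. The reply does not remove the point, because the plan does not adopt the all-three rule either.

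Three stronger readings are tempting, and the documents do not support them:

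- *A false claim about cognitive decline has up to a 14% chance.* That needs independent composites, which the overlap rules out. It also counts false results favouring placebo, whereas hypothesis 1 is directional.
- *One end point was replaced by three.* Sections 1.1 and 1.3 are summaries. They describe a battery covering several domains and do not promise a single global score; 9.6.5.3 can fairly be read as elaborating them.
- *Any one composite suffices as the plan is written.* The plan is silent on this.

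It can also be argued that strict control among secondary end points is a matter of judgement, and that a global gatekeeper penalises an effect confined to one domain. That is fair, and it is why more than one rule is acceptable.

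**Conclusion.** The point holds as an omission: three equally ranked tests bear on a headline hypothesis without an order, a success rule or error control. The wording gap is certain; its numerical size is conditional.

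Under the any-one reading, two-sided 0.05 per composite and inter-test correlations of 0.2-0.5, the family-wise rate is about 8-11%, roughly 1.7 to 2.2 times nominal (8.3/5 to 10.9/5). For false benefit it is about 4-5.5% against 2.5%. The direction does not depend on the exact correlation: some inflation remains unless the composites are practically identical.

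These figures cover the three composite tests only. They are not the error rate for the whole trial, because they leave out the primary-family tests and the treatment-by-time tests.

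The sponsor should correct this, but it does not undermine the design.

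**What to change.** State one rule in 9.6.5.3 before unblinding, together with the significance level. Either of these is sound:

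1. Name the global composite as the lead test at two-sided 0.05; it is the closest to the battery-wide end point of sections 1.1 and 1.3. Test verbal memory and executive function, with Holm across the two, only if the global test succeeds. Otherwise report both as exploratory estimates with confidence intervals.
2. Keep all three co-secondary and apply Holm across them.

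Both need wording only, with no change to data collection. Under option 1 the global test loses no power, but a domain-only result cannot support a claim. Under option 2 a domain-only claim remains possible at some loss of power per composite. For illustration, a test with 80% power at 0.05 has Φ(2.80 - 2.39) = about 66% at the first Holm threshold of 0.0167, and more at the later thresholds. The 80% is assumed.

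Neither option links cognition to the primary end points or covers the treatment-by-time tests. The text should say that control applies within these three tests only.
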